All tests will be two-sided, p-values of less than 0.05 will be considered as evidence of a difference between treatment arms, and conditional effects will be reported. P-values will be reported to four decimal places with p-values less than 0.0001 as <0.0001. All confidence intervals presented will be 95% and two-sided. Exact confidence intervals will be used for binary data, where exact models have been used. Multiple comparisons will be performed and this may increase the probability of observing a statistically significant result by chance. No adjustments will be made to account for multiple testing. The statistical package SAS will be used to conduct analyses.

The key demographics and clinical condition of the participants will be presented for each arm of the trial to describe the cohort. In addition, a summary of transplant characteristics will be presented for each arm of the trial. A CONSORT diagram will be presented to show how participants progressed through the trial.

All analyses and accompanying tables will be presented by the treatment to which the participant was randomised. All odds, hazard and rate ratios will be presented as Plasmalyte arm versus Standard arm. A ratio which is greater than 1 indicates that the odds, hazard or rate of the event is greater in the Plasmalyte arm. 95% confidence intervals will be presented with all ratios.

P-values for regression models will be obtained by comparing models with and without the treatment term using the likelihood ratio test. In analyses where mixed models are performed, the log-likelihood will be estimated using pseudo-likelihood methods.

All analyses will be adjusted for the stratification variables (site and participant weight pre transplant: <20kg and ≥20kg) and donor type: deceased and living, as this was also felt to be an important factor which could affect the outcomes of interest. Site will be

Statistical Analysis Plan

accounted for by including a random effect and participant weight and donor type by a fixed effect in each model.

Although PLUTO is a definitive trial, the total sample size is relatively small, hence:

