- In the adjusted analyses we may observe separation of data points for outcomes with lower event rates. If this occurs, we would initially drop donor type from the model. If this does not resolve the problem, then site will be removed and a fixed effects regression model adjusting for participant weight pre transplant and donor type will be used. If this does not resolve the problem, then we would additionally drop donor type from the fixed effects regression model. If this is not suitable, then an unadjusted analysis will be performed. If the initial model is a mixed logistic regression model, then if site is removed, an exact logistic regression model will be used, where computationally possible. If exact regression is not possible, then a fixed effects logistic regression model with a Firth correction to reduce bias in the parameter estimates will be used. For each analysis, table footnotes will be used to indicate the final model type and the variables adjusted for.
- It is anticipated that in some tables and frequencies, the number presented will be less than 5. It was agreed by the TMG that all data will be presented as observed within the Data Analysis Report (as this report is only shared amongst the trial teams) but within any publications, data less than 5 will be presented as <5.

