3.4 Analysis of secondary outcome measures

Symptoms of acute hyponatraemia (nausea, vomiting, headache, seizures) within the first 72 hours post-transplant

The number and percentage of participants experiencing each symptom will be presented by trial arm and overall. The proportion of participants experiencing each symptom at least once will be compared with exact logistic regression, because the number experiencing these symptoms may be small. The model will be adjusted for donor type (living vs deceased donor) and participant weight (<20kg vs ≥20kg pretransplant).

Statistical Analysis Plan

The degree of fluid overload experienced

This outcome is defined as proportional increase in patient weight between pretransplant weight and maximum weight in the 72 hours post-transplant. The mean proportional weight increase, with standard deviation, will be presented for each trial arm and overall. A Normal linear regression model will be used to assess whether mean proportional weight increase is different between the two treatment arms, adjusting for donor type (living vs deceased donor), participant weight pre transplant (<20kg vs ≥20kg pre-transplant) and transplant centre as a random effect. Residual plots from the normal linear regression will be examined. If there is any evidence of skew or non-constant variance, normal linear regression of log-transformed proportional weight increase will be used to assess whether mean log- proportional weight increase are different between the two treatment arms, adjusting for donor type (living vs deceased donor), participant weight pre transplant (<20kg vs ≥20kg pre-transplant) and transplant centre as a random effect.

Time to discharge from hospital

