4.4 Secondary Outcome table(s)

| Table XX Secondary outcome | me – symptoms of acute hyponatra | aemia | | |
|---|--|--------------------------|----------------|--|
| | Randomise | Randomised Treatment | | |
| | Standard care (n=) | Plasma-Lyte 148 (n=) | Total (n=) | |
| Symptoms of acute hyponatraem | nia within the first 72 hours post-tra | ansplant | , , | |
| Nausea | - | | | |
| N/Total N (%) | | | | |
| OR (95% CI) ¹ | | | | |
| p-value ² | | | | |
| Vomiting | | | | |
| N/Total N (%) | | | | |
| OR (95% CI) ¹ | | | | |
| p-value ² | | | | |
| Headache | | | | |
| N/Total N (%) | | | | |
| OR (95% CI) ¹ | | | | |
| p-value ² | | | | |
| Seizures | | | | |
| N/Total N (%) | | | | |
| OR (95% CI) ¹ | | | | |
| p-value ² | | | | |
| ¹ Adjusted for site, participant weigh | ht pre transplant and donor type. | | | |

² p-value from the likelihood ratio test when including and excluding the treatment term from the model.

³ Per participant

Adjusted for site, participant weight pre transplant and donor type.
 p-value from the likelihood ratio test when including and excluding the treatment term from the model.

Statistical Analysis Plan

| Table XX Secondary outcomes - fluids | | | |
|---|------------------------|--------------------------|----------------|
| | Randomise | ed Treatment | |
| | Standard care (n=) | Plasma-Lyte 148 (n=) | Total (n=) |
| The degree of fluid overload experienced | | | |
| Mean proportional weight increase (Standard Deviation) ¹ | | | |
| Mean difference (95% CI) ² | | | |
| p-value ³ | | | |
| | | | |
| Number of changes in intravenous fluid compos | sition within the firs | st 72 hours post-trans | plant |
| N at least one change /Total N (%) | | | |
| Mean (Standard deviation) number of changes ¹ | | | |
| Rate ratio (95% CI) ^{2,4} | | | |
| p-value ^{3,4} | | | |
| ¹ Unadjusted | | | |

⁴ Adjusted for number of hours the participant was at risk of the event

| Table XX | Secondary outcome – time to discharge | | | |
|--------------|---------------------------------------|------------------------|--------------------------|----------------|
| | | Randomised Treatment | | |
| | | Standard care (n=) | Plasma-Lyte 148 (n=) | Total (n=) |
| Time to disc | harge from hospital (days) | | | • |
| Median (I | QR) ^{1,2} | | | |
| Hazard ra | atio (95% CI) ³ | | | |
| p-value⁴ | | | | |

¹ Unadjusted

⁴ p-value from the likelihood ratio test when including and excluding the treatment term from the model.

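### Where exact logistic regression is used, the SAP makes the interval exact but still takes the p-value from a likelihood ratio test, so with few events the two can contradict each other in the same table row

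*SAP*

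**What the plan says.** Section 3.2 states the general rule: "P-values for regression models will be obtained by comparing models with and without the treatment term using the likelihood ratio test". The same section sets the decision threshold: "All tests will be two-sided, p-values of less than 0.05 will be considered as evidence of a difference between treatment arms". For intervals it adds: "Exact confidence intervals will be used for binary data, where exact models have been used". It says nothing comparable about p-values.

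Exact models enter in two places.

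- In section 3.4, each of the four hyponatraemia symptoms is "compared with exact logistic regression, because the number experiencing these symptoms may be small". That model adjusts for donor type and weight, with no site effect.
- In section 3.2, the steps for separated data say of outcomes planned with mixed logistic regression: "if site is removed, an exact logistic regression model will be used, where computationally possible". Failing that, a Firth-corrected model is used.

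In section 4.4 the p-value rows of the symptom table carry a footnote marker. The p-value footnotes in that section read: "p-value from the likelihood ratio test when including and excluding the treatment term from the model". No part of the SAP mentions an exact p-value.

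**The concern.** Exact logistic regression is chosen when large-sample approximations cannot be trusted. Its inference comes from the distribution of the treatment statistic given the number of events and the covariate totals. A likelihood ratio test comparing models with and without treatment is ordinarily referred to a chi-square distribution, which is a large-sample approximation. As written, the plan takes its interval from one null distribution and its p-value from another, in the sparse data where the two differ most.

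At stake is the reading of rare events such as seizures, or a rare electrolyte abnormality that reaches the fallback. A row could show a p-value below 0.05, which the SAP counts as evidence of a difference, beside an exact interval that includes 1. The reader would have no stated rule for which to believe.

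**Working it through.** **Inputs.** The SAP gives no p-value or event rate for sparse outcomes, so there is no figure of that kind to reproduce. Section 1.6 fixes the arm size: 128 patients before dropout (64 per arm) and 144 after 10% dropout (72 per arm). Check: 128/0.9 = 142.2, so 143, or 144 as an even number. The threshold is 0.05, two-sided (section 3.2). Event counts and true event rates below are assumptions for illustration.

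**A 3-0 split, 64 per arm, likelihood ratio test.** G = 2 × (log-likelihood with treatment − log-likelihood without).

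- With treatment: 3 ln(3/64) + 61 ln(61/64) = −12.109
- Without: 3 ln(3/128) + 125 ln(125/128) = −14.225
- G = 2 × (14.225 − 12.109) = 4.231; on chi-square with 1 df, p = 0.040

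**The same split, exact test.** Given 3 events in total, the chance that all fall in one named arm is C(64,3)/C(128,3) = 41,664/341,376 = 0.122. Two-sided p = 2 × 0.122 = 0.244. The exact lower 95% bound is the odds ratio at which that probability falls to 0.025, which is 0.42. The upper bound is infinite, so the interval includes 1.

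**Is it the choice of likelihood?** No. Under the exact model's own conditional likelihood, the unrestricted maximum for a 3-0 split is 1 and the null value is 0.122. Then −2 ln(0.122) = 4.21, and p is again 0.040. The reference distribution causes the gap.

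**Does adjustment change it?** Assume 144 children spread evenly over arm, weight group and donor type (18 per cell). The adjusted likelihood ratio p for 3-0 is 0.0395 and the exact conditional p is 0.248.

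**Other splits, 64 per arm.**

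| Split | Likelihood ratio p | Exact p | Exact lower 95% bound |
|---|---|---|---|
| 3-0 | 0.040 | 0.244 | 0.42 |
| 4-0 | 0.017 | 0.119 | 0.67 |
| 5-0 | 0.008 | 0.058 | 0.95 |
| 6-1 | 0.041 | 0.115 | 0.75 |
| 6-0 | 0.003 | 0.028 | above 1 |

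The first four rows would each show p<0.05 beside an interval that includes 1. At 6-0 the two agree. Results at 72 per arm are nearly the same.

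**False-positive rate given the event total** (no effect, 64 per arm, all splits enumerated):

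| Events | 2 | 3 | 4 | 5 | 6 | 7 | 8 | 9 | 10 |
|---|---|---|---|---|---|---|---|---|---|
| Likelihood ratio | 0% | 24.4% | 11.9% | 5.8% | 2.8% | 11.5% | 6.2% | 3.3% | 9.6% |

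The exact test rejects 0%, 0%, 1.3% and 1.7% of the time at 3, 4, 7 and 10 events. At 6 and 9 events the two tests reject the same splits.

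**False-positive rate averaged over event counts** (64 per arm, unadjusted):

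| True rate | 0.5% | 1% | 2% | 3% | 4% | 5% | 7% | 10% |
|---|---|---|---|---|---|---|---|---|
| Likelihood ratio | 0.6% | 2.8% | 7.6% | 9.3% | 8.8% | 7.9% | 6.5% | 5.5% |

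From 15% to 50% it lies between 4.8% and 5.6%. The exact test's size is 0.1% at a 2% rate, 0.4% at 3% and 1.2% at 5%.

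**The case against.** **The chi-square reference is inferred.** The SAP never says asymptotic or chi-square. The symptom text in section 3.4 says that the comparison itself is made with exact logistic regression and, unlike the text for the primary outcome and the other electrolyte abnormalities, does not name the likelihood ratio test. One could read it as making the p-value exact too. This stands in part: a reader should not infer that the SAP knowingly prescribes a large-sample test for these outcomes. But the rule in section 3.2 covers regression models without exception and states exactness only for intervals. An analyst who reported an exact p-value would be departing from it.

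**The footnotes are weak evidence of intent.** Footnote 1 of the symptom table claims adjustment for site, which the section 3.4 symptom model omits, so these footnotes look like repeated template text. Section 3.2 also promises footnotes giving the final model and its covariates. Both points are fair, but that promise does not extend to the p-value method, and the template text repeats the same rule.

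**The size is uneven.** A reader might take the 24% at three events as typical. It is not: at 2, 5, 6, 8 and 9 events the rate is between 0% and 6.2%. If nausea, vomiting or headache occur in 10% or more of children, the inflation is negligible.

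**The consequences are limited.** A reader might infer that the trial's safety conclusions or its primary result are at risk. The documents do not support that. Section 3.5 excludes serious adverse events from testing, and seizures are tested only as one of the secondary symptoms. Section 3.2 says that only the primary outcome is powered and warns of chance findings. With 59% against 29.5% assumed, the primary outcome is not sparse. The interval would also sit beside the p-value for the reader to see.

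**Conclusion.** The point holds as an internal conflict in the plan for sparse secondary binary outcomes. It is direct for the four symptoms. For other outcomes it arises only if the separation steps lead to the exact model. Followed as written, with the usual chi-square reference, the plan treats splits of 3-0, 4-0, 5-0 and 6-1 as evidence of a difference when the exact interval includes 1. The average false-positive rate is about 7% to 9% for true event rates of about 2% to 7%, and near or below 5% outside that range.

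This rests on 64 children per arm, no treatment effect and event rates chosen for illustration. The 3-0 result was also checked with adjustment for weight and donor type. No error has been shown in the Firth fallback, and none should be inferred. The point is worth correcting before analysis.

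**What to change.** In section 3.2, after the likelihood ratio rule, add: *Where exact logistic regression is used, for the symptoms or as the fallback for separation, the p-value will be the two-sided exact conditional p-value for treatment, from the same model as the exact confidence interval.* Change the p-value footnote of the symptom table to match, and do the same for any table whose final model is exact.

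The cost is one sentence and the footnotes. The exact p-value comes from the same fit as the interval, so no further data or patients are needed.

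The statistical price is real. The exact test is conservative, with a true size well under 5% for rare events. Even 5-0 would not reach significance (p=0.058), and the smallest all-in-one-arm split that does is 6-0 (p=0.028). Sensitivity to rare harms falls, which the SAP should acknowledge.

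Optionally, name the penalised likelihood ratio test and its matching profile interval for the Firth fallback. That would be a clarification, not a correction.

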3.3 Analysis of primary outcome measures

The number and percentage of participants who experience acute hyponatraemia (defined as plasma sodium concentration <135mmol/L) within 72 hours post-transplant will be presented by trial arm and overall. This will be analysed using a mixed logistic regression model adjusting for donor type (living vs deceased donor), participant weight (<20kg vs ≥20kg pre-transplant) and transplant centre as a random effect. A superiority hypothesis will be tested and the results from the adjusted analysis will be considered the primary analysis. The adjusted odds ratio for treatment, with 95% confidence interval, will be presented from this model, with the p-value from the likelihood ratio test when including and excluding the treatment term from the model. This will be the primary analysis. The median and interquartile range of the number of each event experienced by each participant will also be presented, but no further statistical testing will be conducted on these. As outlined above, this will be analysed using the modified intention to treat population, which includes all participants randomised and transplanted. This outcome will also be analysed in the per protocol population, which additionally excludes those randomised in error, with a protocol deviation, or withdrawn from the trial.

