1.6 Sample size calculation

The sample size required for this trial is 144 participants randomised. Analysis of 76 paediatric transplants performed at Great Ormond Street Hospital between 1 January 2015 and 31 March 2018 showed that 45 children (59%) experienced hyponatraemia within the first 72 hours post-transplant when managed with 0.45% saline 5% glucose fluid (1). This was used as the baseline rate. In the Cochrane systematic review by McNab S et al. (2), a 50% reduction in risk of hyponatraemia was shown. A greater effect size is anticipated because the rate of fluid delivery to children following kidney transplant significantly exceeds maintenance requirements (3). Using the 50% effect size from the Cochrane review, the assumed incidence of hyponatraemia would be reduced to 29.5%. A two-sided test with 90% power, 5% type I error and 1:1 allocation and allowing for two formal interim analyses for harm or benefit would require 128 patients. After allowing for 10% drop out, for example if a transplant cannot proceed due to a positive cross match, the total number of participants required is 144.

2. Data Handling

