https://www.who.int/toolkits/growth-reference-data-for-5to19-years will be used to determine the height percentiles. Heights in cm will be converted to inches by dividing by 2.54 and will utilise the height at transplant. The mean minimum and maximum normalised systolic blood pressure, with standard deviation, will be presented separately for each trial arm and overall, for each day. A repeated measures mixed Normal linear regression will be used to assess whether mean percentiles over the three days are different between the two treatment arms, adjusting for donor type (living vs deceased donor), participant weight pre transplant (<20kg vs ≥20kg pre-transplant) and day of measurement. In addition, two random effects will be included in the model to account for individual participant effects and transplant centre. Residual plots from the normal linear regression will be examined. If there is any evidence of skew or non-constant variance, repeated measures mixed normal linear regression of log-transformed percentile will be used to assess whether mean log-percentile are different between the two treatment arms, adjusting for donor type (living vs deceased donor), participant weight pre transplant (<20kg vs ≥20kg pre-transplant) and participant and transplant centre as random effects.

Number of changes in intravenous fluid composition within the first 72 hours post-transplant

A change to intravenous fluid composition will be defined as any modification to the composition of the fluid administered to the participant. The number of changes in fluid will be counted as follows:

- If the participant is initially given something different to which they were randomised, this will be counted as the first change
- Subsequent changes will be counted based on the fluid being administered before the change.
- Diluent used for drug infusions, will not be counted.

For example:

- if the participant was randomised to standard arm, was first administered Hartmann's solution, then 0.9% sodium chloride, and then Hartmann's solution again, this would be counted as two changes.
- If the participant was randomised to Plasma-Lyte, was first administered 5% glucose, then received Plasma-Lyte 148 and then Plasma-Lyte® 148 & Glucose 5%, this would count as three changes.

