- Non anion-gap acidosis (defined as bicarbonate < 20mmol/L and anion gap < 20mmol/L. Anion gap will be calculated as the sum of sodium and potassium, minus the sum of chloride and bicarbonate)
- Hyperglycaemia (defined as glucose > 5.5 mmol/L)
- Hyperchloraemia (defined as chloride concentration > 107mmol/L)
- Excessive rate of reduction in sodium concentration (defined as >1mmol/L/hour averaged over 6 hours)
- Excessive magnitude of reduction in sodium concentration (defined as > 10mmol/L from pre-transplant level)

Where multiple test results are required to meet the criteria for an abnormality, events will only be identified in either all plasma results or all blood gas results (e.g. determining an excessive magnitude of reduction in sodium concentration will compare plasma sodium results against the pre-transplant plasma sodium, and blood gas sodium results against the pre-transplant blood gas sodium).

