4.9 Figures

Figure XX Consort diagram

[figure not shown]

Figure XX Time to first acute hyponatraemia

A cumulative incidence curve showing the time to first developing acute hyponatraemia (defined as plasma sodium concentration <135mmol/L) within 72 hours post-transplant, by arm. Acute hyponatremia will be considered as the event and death prior to the event will be considered as the competing risk. Although if there are no deaths, the Kaplan-Meier method will be used.

Statistical Analysis Plan

Figure XX Lowest plasma sodium concentration by day

For each participant, the lowest plasma sodium measurement each day will be obtained and of these the median and interquartile range will be plotted by day and treatment arm. These will be plotted as box plots, for baseline and for the three days post-transplant. Any outliers will also be populated.

Figure XX Highest plasma chloride level by day

For each participant, the highest plasma chloride measurement each day will be obtained and of these the median and interquartile range will be plotted by day and treatment arm. These will be plotted as box plots, for baseline and for the three days post-transplant. Any outliers will also be populated.

Figure XX Highest potassium level by day

For each participant, the highest plasma potassium measurement each day will be obtained and of these the median and interquartile range will be plotted by day and treatment arm. These will be plotted as box plots, for baseline and for the three days post-transplant. Any outliers will also be populated.

5. Statistical Analysis Plan Amendments

Revision History:

| Version | Author | Date | Reason for revision |
|---------|-------------|------------|--|
| 1.1 | [name] | 20/12/2022 | Updating sensitivity outcomes to incorporate blood gas results as well as plasma. Updating blood pressure outcome to normalised percentile in Table 4.4 in line with text. Separated secondary outcome tables into multiple smaller tables. Clarified some statistical methods/model fitting criteria, including how the planned models will be modified if issues with model fitting. |
| | | | |
| | | | |
| | | | |
| | | | |

6. References

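### The primary model leaves out pre-transplant plasma sodium, which is scheduled at baseline, and so gives up some precision and protection against chance imbalance

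*SAP*

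**What the plan says.** Section 3.3 defines the primary event as a plasma sodium below 135 mmol/L within 72 hours, with no condition on the starting value. On the model it says: "This will be analysed using a mixed logistic regression model adjusting for donor type (living vs deceased donor), participant weight", with transplant centre as a random effect. Section 3.2 applies the same set (site, weight group, donor type) to all analyses. Donor type was not a stratification factor; section 3.2 adds it because it was thought likely to affect the outcomes.

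The pre-transplant value is already part of the plan:

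- Section 2.1 schedules blood results at the baseline (pre-transplant) visit.
- Section 3.4 defines an excessive fall in sodium relative to the pre-transplant level, and section 3.5 does so for acute severe hyponatraemia.
- Section 3.7 explains that the fall definition "will compare plasma sodium results against the pre-transplant plasma sodium".
- Section 4.9, on the lowest sodium by day, says: "These will be plotted as box plots, for baseline and for the three days post-transplant".

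Baseline sodium does not appear in the sensitivity models (3.7), the imputation variables (3.8) or the baseline table (4.2). No reason is given.

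The blood pressure model in section 3.4 has the same feature. It is fitted "adjusting for donor type (living vs deceased donor), participant weight pre transplant (<20kg vs ≥20kg pre-transplant) and day of measurement", without the baseline systolic pressure that section 4.2 tabulates and section 3.8 lists for imputation.

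**The concern.** The outcome is a threshold on a variable that is also measured before treatment. The baseline value of that variable has at least as good a claim to a place in the model as donor type, by the reasoning section 3.2 uses for donor type.

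Leaving it out has two costs. Some power is given up that needs no extra patients. And with about 64 children per arm, a chance difference in starting sodium passes into the primary odds ratio uncorrected.

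A related matter is that a child already below 135 mmol/L before surgery can count as an acute event, and no analysis sets such children apart.

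**Working it through.** **Inputs.** From section 1.6: "A two-sided test with 90% power, 5% type I error and 1:1 allocation"; control rate 59% ("45 children (59%) experienced hyponatraemia within the first 72 hours post-transplant"); Plasma-Lyte rate 29.5%; and "allowing for two formal interim analyses for harm or benefit would require 128 patients". From section 3.1: O'Brien-Fleming looks at 70 and 100 patients. Assumption, not in the SAP: the within-arm correlation rho between baseline and lowest sodium, varied over a range.

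**1. The plan's own figure.** With d = 0.295 and mean rate 0.4425:

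n = [1.96 √(2 × 0.4425 × 0.5575) + 1.2816 √(0.59 × 0.41 + 0.295 × 0.705)]² / 0.295² = 57.47 per arm.

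Continuity correction: (57.47/4) × [1 + √(1 + 4/(57.47 × 0.295))]² = 64.07 per arm, or 128.1 in total. The interim looks inflate this by 1.015 (equal spacing) to 1.021 (actual spacing), giving 130 to 131, within 3% of 128. Dropout: 128/0.90 = 142.2, so 143, or 144 when made even. The sample size reproduces. Without the continuity correction, power at 64 per arm is 0.929.

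**2. Power with and without the covariate.** Lowest sodium was simulated as L = rho·x + √(1 − rho²)·e, where x is standardised baseline sodium and e is standard normal noise. An event occurs when L falls below an arm-specific cut that gives the stated rates. Logistic likelihood ratio tests were run at 3.841 with 64 per arm (4,000 replicates; 3,000 for the smaller effect). Centre, weight, donor type and interim looks were left out.

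| Rates | rho | Power without | Power with | OR without | OR with |
|---|---|---|---|---|---|
| 59% v 29.5% | 0.2 | 0.931 | 0.939 | 0.286 | 0.270 |
| | 0.3 | 0.934 | 0.942 | 0.286 | 0.259 |
| | 0.4 | 0.925 | 0.947 | 0.289 | 0.247 |
| | 0.5 | 0.927 | 0.956 | 0.289 | 0.227 |
| 59% v 34.5% | 0.3 | 0.797 | 0.825 | 0.360 | 0.336 |
| | 0.5 | 0.808 | 0.874 | 0.358 | 0.290 |

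**3. Validity.** With no treatment effect (rho 0, 0.3, 0.5), the rejection rate is 0.053 to 0.060 without the covariate and 0.052 to 0.056 with it. Both are near nominal.

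**4. Chance imbalance.** The 95% range for a difference in mean baseline sodium is ±1.96 × √(2/64) = ±0.35 SD. At the adverse edge (Plasma-Lyte arm lower):

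| rho | OR without | Power without | OR with | Power with |
|---|---|---|---|---|
| 0.3 | 0.336 | 0.865 | 0.264 | 0.942 |
| 0.5 | 0.384 | 0.756 | 0.231 | 0.950 |

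At the favourable edge the OR without the covariate falls to 0.243 or 0.217, while the adjusted OR stays at 0.267 or 0.224.

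**5. Existing hyponatraemia.** Assume, for illustration, that a share q of children are events in either arm and that risk is halved in the rest. The Plasma-Lyte rate becomes q + (0.59 − q)/2. For q = 5%, 10% and 15% this is 32.0%, 34.5% and 37.0%, and power at 64 per arm is 0.88, 0.80 and 0.71. Restricting to children who start at 135 mmol/L or above, with 64(1 − q) per arm, gives 0.90, 0.85 and 0.80.

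**The case against.** The planned covariate set is legitimate and pre-specified. The test is valid, the sample size reproduces, and power without baseline sodium already exceeds 90% at the design effect. The gain rests on an assumed correlation. At rho 0.3 it is under one point, and the simulations do not estimate the increment over a model that already has centre, weight and donor type. The adverse-edge imbalance at rho 0.3 moves the log odds ratio by ln(0.336/0.286) = 0.16. Its standard error is √[1/(64 × 0.59 × 0.41) + 1/(64 × 0.295 × 0.705)] = 0.37, so the shift is under half a standard error, and the confidence interval already allows for such variation.

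All of this stands, and it limits the size of the point. It does not remove it, because the value is already scheduled and the remedy needs no further patients or data collection. The shift also grows with rho: at 0.5 it is ln(0.384/0.289) = 0.28, about three quarters of a standard error.

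Three practical objections also stand and shape the remedy:

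- Section 3.8 relies on adjustment factors always being known, and a scheduled sodium is not certain to be available for every child.
- Section 3.7 keeps plasma and blood gas results apart where a definition needs several results, so filling gaps from blood gas would sit badly with it.
- Exact logistic regression, the first fallback in section 3.2 once site is removed, may not be workable with a continuous covariate.

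**Conclusion.** The point holds as a modest, low-cost improvement to the primary analysis. Under assumed correlations of 0.2 to 0.5, omitting baseline sodium costs about 1 to 3 points of power at the design effect. At 59% v 34.5% it costs about 3 to 7 points at correlations of 0.3 and 0.5. Stability under chance imbalance is the stronger argument. The simplified simulations make these figures indicative.

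A reader might infer more than the document supports:

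- **That the primary result would be biased or the trial underpowered.** Randomisation protects the test, type I error is near nominal, and 128/144 reproduces.
- **That a child already below 135 mmol/L is an event whatever fluid is given.** Section 1.4 has trial fluid starting intra-operatively, so post-operative samples follow treatment. The SAP does not say how many such children to expect; the shares in step 5 are illustrations.
- **That the covariate would deal with existing hyponatraemia.** It would not, because those children still count as events. Only a restricted analysis addresses them.

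The blood pressure model is a reasonable secondary change, but its effect was not quantified.

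**What to change.** Before unblinded analysis, amend the SAP as follows.

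1. Add pre-transplant plasma sodium as a continuous fixed effect to the primary model in section 3.3, its per-protocol version and the third sensitivity analysis in section 3.7. Define it as the last plasma value before trial fluid starts.
2. State a simple rule for a missing baseline value, for example overall-mean imputation of the covariate with a missing indicator. Do not substitute a blood gas value. Amend the statement in section 3.8 that adjustment factors are always known.
3. In the reduction sequence in section 3.2, keep baseline sodium after donor type and site have been dropped. Go to the Firth model if exact regression is not workable with a continuous covariate.
4. Report baseline sodium by arm in the section 4.2 table.
5. Add a supporting analysis restricted to children with pre-transplant plasma sodium of 135 mmol/L or above.
6. As a secondary change, add baseline systolic pressure, normalised in the same way, to the blood pressure model in section 3.4.

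The cost is SAP wording and a little programming. The main downside is that the target odds ratio changes, because odds ratios are not collapsible: from about 0.29 to 0.26 at rho 0.3, or 0.23 at rho 0.5. Section 3.2 already reports conditional effects, so this fits the plan, but the covariate has to be fixed in advance.
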